Précis: This study aims to discern whether Transcutaneous Electrical Acustimulation (TEA) at acupuncture points ST36 and/or PC6 will relieve the abdominal pain associated with IBS-C. Each study participant will have 5 research visits at the Michigan Medicine GI physiology lab. During these visits, they will undergo a procedure similar to Anal Rectal Manometry performed by the GI physiology lab staff. TEA is similar to this procedure as it uses the barostat device and is performed by the GI physiology lab staff. This device has a rubber catheter that will be inserted 5-15 cm into the rectum of the study participant. Then the GI physiology staff will inflate the catheter. They will ask the study participant when they can sense the catheter. Then the GI physiology staff will continue to inflate the catheter and the study participants feel discomfort (described as the 'urge to defecate'). Then the study participant will be asked to pass the balloon (like they would pass a bowel movement).

The difference between ARM procedure and the study procedure is that there will be stimulation of acupuncture point ST36 which is below the knee cap or stimulation of acupuncture point PC6 which is just above the wrist.

At each visit there will be stimulation of only one of the points at either 100Hz or 25Hz. These are the potential combinations: ST36 100Hz, ST36-25Hz, PC6-100Hz, PC6-25Hz, Sham-TEA.

The frequency and position combination (or sham visit) is randomly assigned. The randomization determines the order in which the study participant moves through the study. Every study participant will, in the end, complete one visit at each frequency and a sham visit. The study participant will also complete surveys at the appointment. Study participants will be compensated for their participation and given a parking pass.

Objectives: Primary: Determine the best stimulation point and frequency for relieving the abdominal pain in study participants with IBS-C.

Secondary: Collect measurements of visceral hypersensitivity in study participants with IBS-C.

Population: 25 study participants, male and females, age ≥ 18 years, IBS-C satisfying Rome IV criteria

Phase: 1

Number of Sites:	1, Michigan Medicine, University of Michigan
Study Duration:	24 Months
Study participant Participation Duration:	Each visit will be 120 minutes long. There will be 5 visits total. The maximum amount of time between visits is 3 weeks. The minimum amount of time between visits is 1 week
Description of Intervention:	The device being studied, the Transcutaneous Electrical Acustimulation (TEA) will give stimulation similar to electro acupuncture at two specific acupuncture points (ST-36 and PC-6) known to impact pain perception. The study team would like to assess if TEA is safe for study participants and will impact the pain perception in study participants with IBS-C.
Estimated Time to Complete Enrollment:	12 Months

Schematic of Study Design:

Table 1: Arm of the study

This study has 1 cohort all study participants are in 1 arm	Sample size: 25 study participants	Intervention: Transcutaneous Electrical Acustimulation (TEA)	Randomization: The order of TEA will be randomized for each study participant.
---	------------------------------------	--	--

See appendix A for the schedule of events table.

2 INTRODUCTION: BACKGROUND INFORMATION AND SCIENTIFIC RATIONALE

2.1 Background Information

- In this project, **we will use a novel transcutaneous electrical acustimulation (TEA) device for treatment of chronic abdominal pain in study participants with Irritable Bowel Syndrome with Constipation (IBS-C)**. This is a device that has stimulating electrodes. The electrodes are placed on acupuncture points that previous studies demonstrate relieve pain related to constipation.
- This therapeutic strategy is called **Neuromodulation**. The process of performing acupuncture via electrical stimulation in place of traditional acupuncture methods is called **electroacupuncture, EA**. The two acupuncture points, acupoints, that have been found to improve autonomic functions impaired in animal models of IBS are points ST-36 and PC6.
- In the human **PC6 is three finger widths above the wrist**. In the human **ST-36 is four finger widths below the knee**.
- The motivation behind this study is to assess the impact of TEA on pain and motility in study participants with IBS-C. If successful, TEA could serve as a non-opioid treatment for pain related to IBS-C.
- The **barostat** is a FDA approved **device (K99 1288)** used in clinical practice and research to study the function and activity of the motor and sensory functions of the gastrointestinal tract. This is a common method used to measure gastric motility (or the movement of food from the mouth through the pharynx (throat), esophagus, stomach, small and large intestines and out of the body). It can monitor volume changes while maintaining a set constant pressure and deliver controlled distensions of gastrointestinal organs. The controlled distension is completed by the device's ability to inflate at the tip of the catheter. In this study, the device will be used in the rectum. This device does not use electricity to stimulate the rectum.
- This device is not being studied. Rather it is used to collect measurements. In this case, we will use the barostat device to monitor the activity in the rectum. The rectum of the GI track thought to be have abnormal activity in study participants with IBS-C, contributing to their symptoms.

Left: image of acupuncture point PC6. Right: image of acupuncture point ST-36.

Top: Image of the rectal barostat balloon, partially inflated. Bottom: Image of the barostat device, control panel.

2.2 Rationale

- The aim of the study is to determine the best TEA stimulation point and parameters for treating the abdominal pain in study participants with IBS based on a well-established measurement of motility, the barostat and the study participant's survey responses.

2.3 Potential Risks and Benefits

2.3.1 Potential Risks

The immediate risks involved with barostat inflation and subsequent rectal distension include:

- Discomfort during the balloon insertion
- Sensation (discomfort) with the balloon inflation which is a variable of the study. The likelihood of this risk is common, up to 100% of participants will experience discomfort. The study team will make the study participant aware of this before consenting to the procedure. The study participant has the right to stop the procedure at any time.
- Bleeding at the site of balloon inflation (in the rectum). The likelihood of this risk is rare, approximate incidence of <1%.

However, the duration of rectal distension is brief and the distension can be immediately terminated upon intolerable pain or discomfort.

The long range risk of barostat inflation is:

- Perforation of the rectum into the peritoneal space, the likelihood of this risk is rare, approximate incidence of <1%.

The risks of electrical stimulation via TEA are:

- Possible allergic reaction to the stimulation electrodes and sensation of electrical stimulation. The likelihood of this risk is rare, approximate incidence of <1%.

However, the stimulation output will be set at a level that is well tolerated by the participant. In very rare occasions, the participant might experience rash or minor infection at the stimulation point that can be treated locally if needed.

The risk involved with the ECG recording:

- Allergic reaction of ECG electrodes. The likelihood of this risk is rare, approximate incidence of <1%

The researchers will try to minimize these risks by having an experienced investigators and lab personnel performing the barostat studies with particular care. The study investigators and our GI Physiology lab staff are well versed in doing these type of procedures. In addition, one of gastroenterologist-physician study investigators will be present/perform the studies or will be readily available on site for consultation/evaluation in case of any study complications or questions.

The rationale behind these risks is that the risks are unlikely and the study participant would receive care

immediately. Moreover, the study team would not be able to collect this data without study participants enduring the risks. Alternative procedures would not provide the same understanding of the influence of TEA for IBS-C study participants.

2.3.2 Known Potential Benefits

A potential benefit for study participant is a reduction in pain related to their IBS-C.

3 Objectives

3.1 Study Objectives

The objectives of this study are as follows:

- To understand the impact of TEA on study participants with IBS-C (reduction of pain related to IBS-C)
- Assess the safety of TEA in study participants with IBS-C
- Refine which (if any) TEA stimulation and location combination delivers the greatest reduction in pain associated with IBS-C

3.2 Study Outcome Measures

The barostat device and study participant survey responses will measure the study outcomes.

3.2.1 Primary Outcome Measures

The barostat device will measure the volume changes in the rectum during controlled distension of the gastrointestinal organs. If the TEA is successful, the study participant's maximum tolerance should increase after TEA compared to their first maximum tolerance of the visit. This will be defined by comparing their maximum tolerance pre and post TEA.

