3.2.2 Secondary Outcome Measures

A secondary outcome of the study will be reviewing the volume and pressure measurements from the barostat device. The surveys will also be reviewed to see if the study participants have a change in their symptoms.

4 Study Design

This is a placebo-controlled trial. The placebo is the sham-TEA visit. The study will recruit 25 study participants with IBS-C. These study participants will be recruited from the UM Health Research Recruiting Registry (UM HealthResearch.org), Michigan Bowel Control Program (MBCP), Functional Bowel Disease (FBD), and the study team will screen the gastroenterology clinic schedules via MiChart.

This is a phase 1 trial. This study will only occur at the University of Michigan. There is only one group/arm of study participants. The study team plans to complete enrollment within 12 months of beginning to the study. Study participant participation will be at a minimum 5 weeks (1 week between

visits) and at a maximum 15 weeks (3 weeks between each visit). The test agent is the novel TEA device.

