4.1 Schedule of Events for Each Visit

Every visit is the same and will follow the steps detailed below, with the exception of the first visit which will include the informed consent process. At visit one, the study team will randomly generate the stimulations schedule unique to each study participant; this is the order of locations and currents by using a random generator. For example, ST36-100Hz, ST36-25Hz, PC6-100Hz, PC6-25Hz and Sham-TEA.

48 Hours prior to the visit: The study participants will not take any medications known to affect the gut or pain perception.

8:00 pm on the night before the visit: The study participants begin fasting for their visit the next day. Study participants can still drink water. Study participants cannot drink coffee, tea, juices or eat any food items.

Day of the Visit:

Study participants will come to the study location, the Gastrointestinal Physiology Lab in University of Michigan. The visit will take place in one of the private rooms within the lab. **If the study participant is a women of child bearing potential:** She will complete a pregnancy test provided by the study team. If her pregnancy test is positive, she will be excluded from further participation in the study and will not complete the visit.

Rome IV Criteria for Irritable Bowel Syndrome: Upon arrival for every visit, the study participant will complete the Rome IV Criteria for Irritable Bowel Syndrome survey.

Enema: The study participant will be given a rectal enema to clean the rectum. Then the study participant will undress from the bottom down and be given a gown and sheets for comfort and privacy.

Position the study participant: The study participant will be asked to lie down on the medical examination table on one side and bring his or her knees up to the chest, similar to the fetal position. The table has rails that will protect the study participant from falling. The staff may use pillows to adjust and secure the study participant as well as for comfort.

Electrode Placement: The GI physiology laboratory staff will place two electrocardiogram (ECG) electrodes from of the TEA device on the subject's skin, one on the wrists at location PC6 and the other

Fig.1: Locations of PC6 and ST36.

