on upper leg below the knee at location ST36. These two electrodes will be used for delivering weak electrical current stimulation. The electric current and stimulating electrode location is determined by that study participant's randomized stimulation schedule. Electrodes will be placed at both locations at each visit.

An additional three ECG electrodes connected to the ECG machine will be placed on the study participant's skin, one on the manubrium of sternum, one above the breastbone and one on the study participant's right chest. These three electrodes will be used for recording the ECG. Before the placement of each of the 5 electrodes, the skin area where the electrodes to be placed will be carefully cleaned using skin-prep materials.

[figure not shown]

Fig.2: Locations of ECG electrodes to read electrocardiogram.

Baseline data collection with the Barostat:

The Barostat is an FDA-Approved device that measures pressure in the rectum. The device has a thin and flexible polyvinyl catheter (PVC) will be placed 5-15 cm into the study participant's rectum. Once placed, this catheter will be in the rectum for the remainder of the visit.

Rest - 15 Minutes

While the study participant is at rest, baseline data will be collected for 15 minutes.

Inflation with the Barostat:

The GI physiology lab staff will inflate a small balloon at the tip of the catheter and ask the study participant to assess the sensation. During this period, the study participant will be asked to take a note of their first sensation, urge to defecate and maximum tolerance; meanwhile, the study participant will also be asked to report the scale of pain or discomfort during the process of the balloon distention. The study participant will complete the Visual analog Scale Pain Score during inflation.

Maximum Tolerance:

Once the maximum tolerance is reached, the inflation will stop and the air will be removed.

TEA – 15 minutes

One of the randomly assigned TEA methods (or sham-TEA) will be performed for 15 minutes.

Inflation with the Barostat and TEA:

Then the inflation process described above will be repeated while applying the TEA. The study participant may sense the weak electrical stimulation. If the stimulation intensity is uncomfortable for the study participant, the stimulation will be set a level where the study participant feels comfortable. This will be noted in the visit summary. The study participant will complete the Visual Analog Scale Pain Score during inflation.

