5.4 Treatment Assignment Procedures

5.4.1 Randomization Procedures

Prior to the first visit, the order of TEA stimulation at the visits will be randomly assigned to each study participant. Every study participant will undergo every TEA combination (For example, ST36-100Hz, ST36-25Hz, PC6-100Hz, PC6-25Hz and Sham-TEA).

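### The primary outcome reads a within-visit rise in maximum tolerance as a TEA effect, with no named comparison to sham, so a repeat-inflation or placebo shift could mimic or hide an effect

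*Combined protocol and SAP*

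**What the plan says.** Section 3.2.1 (Primary Outcome Measures) says that if TEA is successful, the "maximum tolerance should increase after TEA compared to their first maximum tolerance of the visit". It continues: "This will be defined by comparing their maximum tolerance pre and post TEA". Sham is not mentioned there.

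Section 4.1 fixes the sequence within a visit. A first inflation without stimulation runs to maximum tolerance. Then "One of the randomly assigned TEA methods (or sham-TEA) will be performed for 15 minutes". After that, "Then the inflation process described above will be repeated while applying the TEA". Apart from consent at visit 1, "Every visit is the same and will follow the steps detailed below", so the sham visit has the same two inflations. (Section 3.2.1 speaks of a measurement after TEA; Section 4.1 takes it during TEA.)

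Randomisation acts across visits only: Section 5.4.1 says "the order of TEA stimulation at the visits will be randomly assigned to each study participant". Section 4 (Study Design) states: "This is a placebo-controlled trial. The placebo is the sham-TEA visit".

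The opening of Section 10 plans an ANOVA among four sessions, although the design has five. Section 10.3 repeats the plan without giving a number. Both apply Tukey's test to differences between stimulation points and between parameter sets. Neither names a contrast of an active modality with sham.

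**The concern.** Within an active visit, receiving TEA and being inflated for the second time always coincide. Familiarity with the procedure, a rectum that has already been distended once, sensitisation, or a response to the expectation of treatment could each move the second reading. The pre/post rise is the sum of these and any TEA effect. Section 3.2.1 names only TEA as the explanation.

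At stake is the question of whether any modality works. The third objective in Section 3.1 allows that no combination may do so, and Section 10.1 hypothesises that TEA will be effective. An upward shift would make an inert modality look effective. A downward shift would conceal one that works. The sham visit holds the data needed to separate these, but no stated comparison uses it for that purpose.

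**Working it through.** **The plan's own figure.** Section 10.2 needs 20 completers and allows 20% dropout: 20 / (1 − 0.20) = 25, as stated. The 20 itself has no stated effect size, SD, alpha or power, so it cannot be re-derived.

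**What each comparison estimates.** Let D be second-inflation minus first-inflation maximum tolerance at one visit. Write its mean as s + τ at an active visit and s at the sham visit. Here s is the repeat-inflation shift plus placebo response, assumed equal at all visits, and τ is the TEA effect.

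- Pre/post at one active visit: s + τ
- Active A minus active B: (s + τA) − (s + τB) = τA − τB
- Active minus sham: (s + τ) − s = τ

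Only the first carries s. The ranking of modalities does not.

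**Illustrative size.** Assumptions, none of them in the documents: a paired two-sided 5% test, n = 20, TEA inert (τ = 0), s = d standard deviations of D, normal changes, and correlation 0.3 between a participant's changes at different visits where several visits are combined. For one modality,

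P(significant rise) = 1 − F(2.093; 19 df, noncentrality d√20), with F the noncentral t distribution.

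| Shift d (SD) | d√20 | Pre/post rise significant, one modality | At least one of four, pre/post | One modality, tested against sham |
|---|---|---|---|---|
| 0 | 0 | 2.5% | about 9% | 2.5% |
| 0.1 | 0.447 | 6% | about 20% | 2.5% |
| 0.25 | 1.118 | 18% | 48% | 2.5% |
| 0.5 | 2.236 | 56% | 91% | 2.5% |
| 0.8 | 3.578 | 92% | over 99% | 2.5% |

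The third column is exact under the assumptions, and the fourth is simulated. The simulated sham visit shows a significant pre/post rise as often as an inert active visit. The last column follows because s cancels. Even against sham, at least one of four inert modalities is significant in about 8% of simulated trials without a multiplicity adjustment.

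**The opposite direction.** Take τ = +0.5 SD and s = −0.5 SD. The pre/post mean is 0, so a significant rise occurs 2.5% of the time. Against sham the standardised effect is 0.5 / √(2 × 0.7) = 0.5 / 1.18 = 0.42, and power is 43%.

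**Precision cost.** Var(D active − D sham) = 2(1 − ρ)Var(D), so the interval widens by √(2(1 − ρ)): 1.41 at ρ = 0, 1.18 at ρ = 0.3 and 1.0 at ρ = 0.5.

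**The case against.** The strongest reply is that Section 3.2.1 states an expectation (a successful TEA should be followed by a rise) and not the converse. It sits under outcome measures, has no test, alpha or threshold, and its last sentence can be read as defining only the variable. The analysis is in Section 10.3, which compares outcomes among sessions. Section 10.2.1 counts five sessions, and Section 10.2 counts four modalities and one placebo. Sections 10.2 and 10.2.2 say that this is a pilot that does not assess efficacy, and the primary objective in the protocol summary is to find the best point and frequency.

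Much of this stands. A reader might infer that the plan formally declares an inert modality successful. The documents do not support that: no pre/post test or decision rule is specified, and the test behind the percentages above is assumed. A reader might also infer that TEA is confounded with inflation order throughout the trial. It is not. The confounding exists only within a visit read without sham, because the sham visit has a second inflation without active TEA. The ranking of modalities is unaffected by a common shift.

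What does not stand is that Section 10 already closes the gap. An ANOVA over all five sessions would include sham, but the section's opening says four, and the pairwise comparisons listed leave sham out. The only description of success remains a pre/post rise, while the objectives and hypothesis still ask whether TEA works at all.

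**Conclusion.** The concern holds within limits. The primary outcome, read with the comparisons the plan names, cannot separate a TEA effect from a repeat-inflation or placebo shift, so it cannot support a statement that a given modality raised tolerance. The choice among the four modalities is not biased by a shift common to all visits.

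The size is unknown, because the documents give neither the magnitude nor the direction of any shift. Under the assumed test, the effect runs from none (2.5% at no shift) through small (6% at 0.1 SD) to severe (92% at 0.8 SD). The at-least-one figures should be read against their no-shift baseline of about 9%. The cancellation against sham assumes the same shift at active and sham visits.

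This should be fixed before analysis. It does not invalidate the trial, since the data that resolve it are already to be collected.

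**What to change.** In Section 3.2.1, keep the within-visit change in maximum tolerance as the variable. Add that any statement that a modality raised tolerance rests on the mean within-participant difference: change at the active visit minus change at the same participant's sham visit. State that a rise within an active visit alone is not evidence of a TEA effect.

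In Sections 10 and 10.3, specify a repeated-measures analysis over all five sessions. Name the four active-versus-sham contrasts, give each a 95% CI and test, and adjust for multiplicity (for example Dunnett). Report the sham-visit change with its own 95% CI.

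The contrast must be a tested mean. A rule that only asks whether the active change exceeds the sham change would not do: with five exchangeable changes, sham is the largest with probability 1/5, so at least one of four inert modalities would pass 1 − 1/5 = 80% of the time.

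The cost is wording and analysis code, with no new visits or data. The interval is wider than the raw pre/post interval by the factor shown above (1.41 to 1.0 for correlations of 0 to 0.5), before the multiplicity adjustment.
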